4 GENERAL STATISTICAL METHODS

4.1 Analysis Sets

4.1.1 Enrolled Cohort

A subject is considered enrolled after signing the study-specific Informed Consent Form (ICF). Patients who sign the ICF but subsequently do not meet one or more of the selection criteria will be considered screen failures and will be excluded from the study.

4.1.2 Intent-to-Treat Cohort (ITT)

This cohort consists of those enrolled patients who meet all inclusion/exclusion criteria and are subsequently randomized.

4.1.3 Per-Protocol Cohort (PP)

The per-protocol cohort is a subset of the ITT subjects who are treated per protocol post randomization with no major protocol deviations (ICH E9 definitions).

5 ADDITIONAL DATA ANALYSES

5.1 Secondary Endpoints

The following will be recorded as secondary outcomes during baseline and follow-up procedures:

- Evaluation of all serious adverse events (SAEs) including all deaths (related and unrelated), severity, onset, time to resolution related to the DSC devices and/or procedure and/or the ERC procedure through 30 days post procedure.
- Radiation exposure to the patient (total fluoroscopy time, total radiation dose, Dose Area Product (DAP), effective dose), from duodenoscope in to completion of stone clearance, not including the validation DSC procedure in ERC arm and ERC procedure in DSC arm.

Form/Template 90702621 Rev/Ver AE < Non-Complex Biliary Stones RCT, document 92232577, Rev/Ver AA > Page 10 of 13

• Duration of procedure defined as time from duodenoscope in to completion of stone clearance, not including the validation DSC procedure in ERC arm and ERC procedure in DSC arm.

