- If clear fluid is aspirated, this may indicate that the pancreatic duct has been accessed. Re-attempt to access the bile duct. If no fluid is aspirated, or if there is remaining uncertainty over which duct was accessed, physicians if they wish, may use a brief tap on the fluoroscopy pedal to assess whether the guidewire appears to be in the bile duct. Alternatively, they may proceed to an early double wire and/or transpancreatic septotomy cannulation technique. They MUST proceed to double wire and/or transpancreatic septotomy cannulation techniques if fluoroscopy-free cannulation failure persists for 15 minutes. If brief fluoroscopy is used to confirm biliary cannulation, then the case is considered a primary endpoint failure, but the DSC technique for stone evaluation and clearance may be continued. Secondary endpoints will be assessed in these patients, including patient radiation exposure.
- If initial fluoroscopy-free cannulation failure persists for 15 minutes, a double wire and/or transpancreatic septotomy cannulation technique should be attempted.
- If cannulation failure persists despite these advanced cannulation techniques for an additional 15 minutes, this will be considered a **cannulation failure**. The patient will **crossover to the ERC arm** where these cannulation techniques will be continued with full fluoroscopy support. If cannulation in the ERC arm fails despite use of fluoroscopy and basic/advanced cannulation techniques for an additional 15 min then participating institutions may then proceed with their standard of care interventions at this point. Use of needle-knife other than for visibly impacted stones will be considered a cannulation failure for these crossover patients.
- Patients will be followed through 30 days post index procedure as indicated in the follow-up schedule.
- 3. After fluoroscopy-free cannulation succeeds, biliary sphincterotomy will be performed. Additional papillary large balloon dilation can be performed if the sphincterotomy is felt to be inadequate
- 4. The sphincterotome will be exchanged for the SpyGlass cholangioscope over the guidewire.
- 5. The cholangioscope will be advanced into the bile duct up to the bifurcation (hilum) and distance from ampulla to the bifurcation (hilum) will be noted. (Adhesive tapes placed on SpyGlass shaft where it exits the duodenoscope working channel when cholangioscope is at the bifurcation, and again when it just exits ampulla will allow measurement of this distance).

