- 15. Stones visualized at cholangioscopy may also be captured and retrieved sequentially using the SpyGlass[™] Retrieval Basket, commencing distally and progressing proximally to the hilum as with balloon extraction. Extracted stones will be counted. If stone capture is difficult using the basket, the endoscopist may switch to balloon extraction at any point. Where retrieval is successful using purely SpyGlass[™] Retrieval Basket alone (without need for balloon catheter), or if retrieval using SpyGlass[™] Retrieval Basket is utilized for the final visualized stone, saline irrigation (Step 12) and cholangioscope reinsertion (Steps 13/14) will not be necessary.
- 16. EHL or LL may be performed for unexpectedly large/complex stones.
 - If stone clearance fails due to size/shape of the stone(s), electro-hydraulic lithotripsy (EHL) or laser lithotripsy (LL) can be performed.
 - If stone clearance still fails **stone extraction failure** will have occurred. However, participating institutions may proceed with their standard of care interventions at this point, including ERC with mechanical lithotripsy or stent

placement followed by repeat ERC on another day. Patients will be followed through 30 days post index procedure as indicated in the follow-up schedule.

Post DSC validation by ERC:

- 17. An occlusion cholangiogram will be performed using the stone extraction balloon catheter and presence or absence of filling defects will be documented.
- 18. If filling defects are noted, then balloon sweeps of the bile duct will be performed to determine if the filling defects are "missed" bile duct stones or simply air bubbles.

The number of "missed stones" > 5 mm per endoscopist's estimate will be documented.

8.7. 24-Hour, 7-Day, and 30-Day Follow-up

The following data will be collected for all subjects (including Roll-in cases) during these follow up periods:

- Phone call to patient
- Serious Adverse Events, all events of Cholangitis, Pancreatitis, Perforation, and Bleeding, and Device Events, including discharge summaries for any device-related hospitalizations.

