1 PROTOCOL SUMMARY

[figure not shown]
Г

E7131 – Non-Complex Biliary Stones DSC vs ERC RCT		
Study Objective	To prospectively compare non-complex biliary stone clearance using fluoroscopy/radiation-free direct solitary cholangioscopy (DSC) utilizing the SpyGlass TM system with non-complex biliary stone clearance using standard endoscopic retrograde cholangiography (ERC).	
Indication(s) for Use	 SpyGlassTM DS Digital Controller is intended to provide illumination and receive, process, and output images from the SpyScopeTM DS Access and Delivery Catheter for diagnostic and therapeutic applications during endoscopic procedures in the pancreatico-biliary system including the hepatic ducts. SpyScopeTM DS Access and Delivery Catheter is intended to provide direct visualization and to guide both optical and accessory devices for diagnostic and therapeutic applications during endoscopic procedures in the pancreatico-biliary system including the hepatic ducts. The following devices will be available upon commercialization: SpyScopeTM DS II Access and Delivery Catheter is intended to provide direct visualization and to guide both optical and accessory devices for diagnostic and therapeutic applications: SpyScopeTM DS II Access and Delivery Catheter is intended to provide direct visualization and to guide both optical and accessory devices for diagnostic and therapeutic applications during endoscopic procedures in the pancreatico-biliary system including the hepatic ducts. SpyScopeTM DS II Access and Delivery Catheter is intended to provide direct visualization and to guide both optical and accessory devices for diagnostic and therapeutic applications during endoscopic procedures in the pancreatico-biliary system including the hepatic ducts. SpyGlassTM Retrieval Basket is indicated for the endoscopic removal of stones, stone fragments, or foreign bodies in the pancreaticobiliary system. SpyGlassTM Retrieval Snare is indicated for the endoscopic retrieval of foreign bodies in the 	
Device	SpyGlass™ Digital System	
Study Design	 Prospective Consecutive cases Multi-center Randomized 1:1 ratio: Group A (ERC arm): Clearance of bile duct stones using standard-of-practice ERCP techniques 	

E/131	 Non-Complex Biliary Stones DSC vs ERC RCT Group B (DSC arm): Clearance of bile duct stones using DSC techniques Block-randomization by site Non-inferiority hypothesis Validation of stone clearance by ERC in DSC arm and by DSC in ERC arm. 	

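### The radiation and duration definitions can be read to leave out rescue ERC in patients randomised to DSC

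*SAP*

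**What the plan says.** SAP 5.1 lists patient radiation exposure and procedure duration as secondary endpoints. Both are measured "from duodenoscope in to completion of stone clearance", "not including the validation DSC procedure in ERC arm and ERC procedure in DSC arm". The same clause is attached to both endpoints in the SAP synopsis (section 1), the Protocol synopsis and Protocol 4.2. In each place the word 'validation' stands once, before the DSC procedure.

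Protocol 8.6, Group B, provides for three kinds of ERC in a patient randomised to DSC:

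- **Validation (steps 17 and 18).** After DSC, "An occlusion cholangiogram will be performed using the stone extraction balloon catheter and presence or absence of filling defects will be documented".
- **Rescue after cannulation failure (step 2).** The patient is to "crossover to the ERC arm", "where these cannulation techniques will be continued with full fluoroscopy support".
- **Rescue after extraction failure (step 16).** The site may go on to its standard care, which can include ERC with mechanical lithotripsy.

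For patients in whom a brief fluoroscopy tap was used to confirm cannulation, step 2 adds: "Secondary endpoints will be assessed in these patients, including patient radiation exposure". No matching sentence covers either rescue group. SAP 4.1.2 defines the intent-to-treat cohort, but SAP 5.1 does not say which analysis set, or which arm for crossovers, applies to the secondary endpoints.

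**The concern.** Sparing patients radiation is the stated reason for studying DSC (Protocol 1 and 5.3). Fluoroscopy and time used because DSC failed are part of the cost of starting with DSC, so they belong in the DSC arm. If rescue ERC is left out under the clause, or credited to the ERC arm because of the crossover wording, the radiation benefit looks larger and the procedure shorter than they were for the patients randomised.

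The written crossover runs only from DSC to ERC. The literal clause is also uneven. Rescue cholangioscopy after extraction failure in the ERC arm (Protocol 8.6, Group A, step 8) is not validation DSC, so the clause does not remove it, whereas rescue ERC in the DSC arm could be removed. With both readings open, the choice could be made after the data have been seen.

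**Working it through.** **1. The plan's own figure.** The only design figure is the sample size: 125 per arm, 90% clearance in both arms, 10% margin, one-sided alpha 0.05, 80% power (SAP 3.1.2). An exact unconditional test ordered on the restricted-MLE score statistic has size 0.0495 and power 0.817 at 125 per arm, so the stated figure is reproduced. It concerns the primary endpoint and is not touched by this clause. The documents give no figure for radiation, duration, rescue rate or rescue time.

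**2. What each reading does to ERC in a DSC-randomised patient.**

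| ERC in a DSC-randomised patient | Validation-only reading | Literal reading | Crossover booked to the ERC arm |
|---|---|---|---|
| Validation cholangiogram | left out | left out | left out |
| Rescue after cannulation failure | counted, DSC arm | left out | counted, ERC arm |
| Rescue after extraction failure, index session | counted, DSC arm | left out | crossover label not used |

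The design line "Validation of stone clearance by ERC in DSC arm and by DSC in ERC arm" (SAP 1, also in the Protocol synopsis) supports the validation-only reading. On the other side, the window already ends at clearance and DSC-arm validation comes after clearance. A validation-only exclusion therefore removes little that the window had not already left out, which leaves room for the wider reading without proving it.

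**3. Time that stays in under the literal reading.** Advanced cannulation techniques are required "If initial fluoroscopy-free cannulation failure persists for 15 minutes", and crossover follows a further 15 minutes of failure. So 15 + 15 = about 30 minutes precede the rescue and remain inside the duration window.

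**4. Radiation (assumed inputs).** Let c be the share of DSC patients with rescue ERC and m their dose as a multiple of the ERC-arm mean. Take the other DSC patients as near zero before clearance; brief taps would raise this slightly.

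DSC mean ÷ ERC mean = c × m if rescue is counted, and about 0 if it is left out.

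- c = 0.03, m = 1: 125 × 0.03 = 3.75 (about 4 patients); ratio 3%; reduction 97%.
- c = 0.10, m = 1: 125 × 0.10 = 12.5 (about 13 patients); ratio 10%; reduction 90%.
- c = 0.10, m = 2: ratio 20%; reduction 80%.

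Moving the crossovers to the ERC arm at m = 1 leaves the ERC mean as it was, for example (125 + 12.5) ÷ 137.5 = 1, and leaves DSC near 0. The contrast is the same as if they were left out.

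The only anchor for c is Protocol 1: 93% and 90% clearance in two earlier series, so 7% to 10% not cleared for any reason. That is a loose upper proxy for rescue.

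**5. Duration (assumed inputs).** If only the rescue segment, lasting r minutes, leaves the DSC arm, the DSC mean is understated by c × r:

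- 0.03 × 15 = 0.45 minutes.
- 0.10 × 45 = 4.5 minutes.

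**The case against.** The strongest reply is that this is an untidy phrase with a clear meaning. One 'validation' can govern both coordinated procedures, the design line pairs ERC and DSC only as mutual validation, and Protocol 8.6 has a matching validation step. The brief-tap sentence shows an intention to count radiation in failed DSC cases, and silence about crossovers is not a rule that excludes them. This makes validation-only the likelier intent, but no text states it for rescue cases.

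A second reply is that the crossover wording undercuts the literal reading: if the patient is now in the ERC arm, the rescue is not an ERC procedure in the DSC arm. That is fair, and these are two separate routes. Both take rescue fluoroscopy out of the DSC arm.

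Third, uncounted radiation is not confined to DSC. Stones found at validation in the ERC arm are removed with fluoroscopy (Group A, step 10) after clearance was deemed complete, so that exposure also falls outside the window. This stands, and the point should not be put as affecting only one arm.

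Fourth, the size is assumed, and a fall from near 100% to 90% or 97% would not change the qualitative message. No hypothesis or formal test is planned for these endpoints. That stands too, and limits the weight of the point.

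**Conclusion.** The wording is ambiguous on a comparison central to the trial's rationale, and nothing else in the protocol or SAP settles it. Assuming 3% to 10% rescue at the average ERC dose, the DSC mean is about 3% to 10% of the ERC mean rather than near 0%. Assuming 15 to 45 minutes of rescue, mean duration shifts by about 0.5 to 4.5 minutes. The primary endpoint and sample size do not change.

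A reader might infer three stronger things that the documents do not support:

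- That the clause definitely removes rescue ERC. It is one of two readings, and the less likely intent.
- That rescue cases are shown to be the longest in the arm. This is plausible for some, but no figures are given, and extraction failures could run longer than crossovers.
- That almost none of the rescue cases' duration is counted. The roughly 30 minutes of cannulation before crossover stays in under the literal clause; only radiation could fall to near zero.

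**What to change.** Replace the clause for both endpoints in all four places (Protocol synopsis, Protocol 4.2, SAP 1 and SAP 5.1; 2 × 4 = 8 edits) with:

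> not including the post-clearance validation DSC in the ERC arm or the post-clearance validation ERC (Protocol 8.6, steps 17–18) in the DSC arm; fluoroscopy, dose and time from any index-session rescue ERC before clearance are included and analysed in the arm to which the patient was randomised.

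Report the number of crossover and other rescue cases, with their radiation and duration, separately.

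Two additions make this workable. State where the window ends for patients not cleared in the index session; removal of the duodenoscope is already time-stamped. Record radiation and time separately for the assigned procedure, rescue and validation, because Protocol 8.6 lists one radiation total per patient and no time stamp for crossover or start of validation.

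The cost is the text edits and a few data fields. The small downside is that the DSC radiation and duration figures become slightly less favourable. Clinical management does not change.

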5.2 Baseline Data

Baseline data will be summarized using but not limited to the following variables: subject demographics, medical history, and history of prior ERCP or sphincterotomy. Descriptive statistics (e.g., mean, standard deviation, n, minimum, maximum) will be reported for continuous variables and frequency tables for discrete variables.

5.3 Procedure Data

Procedure data, such as cannulation success, biliary sphincterotomy and stone removal will be collected and reported using descriptive statistics (e.g., mean, standard deviation, n, minimum, maximum) for continuous variables and frequency tables for discrete variables.

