5.4 Post-Procedure Data

Post-procedure data will be collected at 24 hours, 7 days, and 30 days, and will be summarized using descriptive statistics (e.g., mean, standard deviation, n, minimum, maximum) for continuous variables and frequency tables for discrete variables.

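### No between-arm estimate or interval is planned for radiation, duration or safety, and the summaries named would describe DSC-arm radiation poorly

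*SAP*

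**What the plan says.** SAP 5.1 introduces the secondary endpoints with "The following will be recorded as secondary outcomes during baseline and follow-up procedures" and then lists three: serious adverse events through 30 days; "Radiation exposure to the patient (total fluoroscopy time, total radiation dose, Dose Area Product (DAP), effective dose), from duodenoscope in" to the end of stone clearance, leaving out the validation procedure; and "Duration of procedure defined as time from duodenoscope in to completion of stone clearance", with the same exclusion. No analysis follows the list.

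Two general sentences can cover these outcomes. Procedure data are to be "reported using descriptive statistics (e.g., mean, standard deviation, n, minimum, maximum) for continuous variables", with frequency tables for discrete ones (SAP 5.3, same text in Protocol 9.3.2). Follow-up data "will be summarized using descriptive statistics (e.g., mean, standard deviation, n, minimum, maximum" (SAP 5.4). Neither names radiation or duration. SAP 7.3 adds that binary event rates are per patient.

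Selected secondary endpoints appear again only in the tabulation by gender (SAP 5.6) and the learning-curve model (SAP 5.9). Neither names treatment arm as a factor. The multivariable analyses (SAP 5.8) concern the primary endpoint.

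Protocol 8.6 gives two routes by which a DSC patient can receive fluoroscopy before validation. The first is a short check of the guidewire: "If brief fluoroscopy is used to confirm biliary cannulation, then the case is considered a primary endpoint failure", with radiation still assessed in those patients. The second is crossover after failed cannulation, "where these cannulation techniques will be continued with full fluoroscopy support".

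**The concern.** Protocol 1 and 5.3 justify the trial largely by the wish to reduce or remove radiation, and Protocol 16.3 names it among the anticipated benefits. The trial randomises 250 patients, so it can estimate the reduction without bias and with a stated precision. The plan does not ask for that estimate. The same holds for procedure time and for harm. Separate columns of percentages, with no difference and no interval, invite a reader to take similar-looking rates as evidence of similar safety.

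The kind of summary also matters for DSC-arm radiation. The measurement window leaves out the validation cholangiogram, so a DSC procedure completed without fluoroscopy scores exactly zero. Guidewire checks and crossovers score above zero. A mean and SD of such a mixture hide both the share of patients exposed and the size of their exposure. The study is not blinded (Protocol 8.5), so if the summary is left open it can be chosen after the results by arm are known.

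**Working it through.** **1. The plan's own figure.** The only size or power statement is for the primary endpoint (SAP 3.1.2): 90% clearance in both arms, margin 10 points, one-sided alpha 0.05, power 80%, 125 per arm. An exact unconditional test ordered on the Farrington-Manning score statistic gives 81.7% power at 125 per arm, with attained size 0.0495. The figure is reproduced, and nothing below disturbs it. No precision figure is given for any secondary endpoint.

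**2. DSC-arm radiation: mean and SD.** The documents do not give the share of DSC patients exposed (q) or the spread of their values. Assume q from 5% to 30% and a coefficient of variation of 1 among the exposed. For a mixture of zeros and positive values, SD/mean = √((1 + CV²)/q − 1) = √(2/q − 1), whatever the unit.

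| Exposed share q (assumed) | SD/mean | Median |
|---|---|---|
| 5% | √39 = 6.2 | 0 |
| 10% | √19 = 4.4 | 0 |
| 20% | √9 = 3.0 | 0 |
| 30% | √5.67 = 2.4 | 0 |

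**3. Median and quartiles are no cure.** Below 25% exposed, the median and both quartiles are all 0. Below 50%, the median is still 0. A Hodges-Lehmann difference for radiation would add little. With 12 of 125 exposed, 113/125 = 90.4% of the pairwise differences are an ERC value minus zero, so the estimate nearly repeats the ERC median.

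**4. What is informative.** The proportion exposed, with an exact 95% interval, remains useful over the whole range (illustrative counts out of 125):

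- 6 exposed: 4.8% (1.8% to 10.2%)
- 12 exposed: 9.6% (5.1% to 16.2%)
- 37 exposed: 29.6% (21.8% to 38.4%)

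The difference in means also stays meaningful with many zeros, because it is the average radiation saved per patient.

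**5. Safety.** Half-width of a 95% interval for a risk difference with a common rate p and 125 per arm: 1.96 × √(2p(1 − p)/125).

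- p = 5%: 1.96 × √(0.095/125) = 5.4 points
- p = 10%: 1.96 × √(0.18/125) = 7.4 points

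Both rates are assumptions, but they are in line with the two series in Protocol 1. Pancreatitis occurred in 4 of 81 (4.9%). All reported complications came to 4 + 3 + 1 = 8 of 81 (9.9%) if each was in a different patient.

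**6. Duration.** The half-width for a difference in means is 1.96 × √(2/125) = 0.25 SD. The documents give no SD, so this cannot be turned into minutes.

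**The case against.** The strongest reply has four parts.

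First, the list in SAP 5.3 begins with e.g., and frequency tables are allowed. Medians, or a yes/no table of fluoroscopy use, would fit without an amendment. A reader might infer that the SAP binds the analysis to mean and SD. It does not: the plan under-specifies the summary. This reply does not reach the missing contrast between arms.

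Second, a reader might infer that the radiation-free claim rests on these summaries. It does not. The primary endpoint requires clearance by fluoroscopy-free cholangioscopy in the DSC arm, and a brief fluoroscopic check makes the case a failure. Fluoroscopy-free success therefore has a test, a margin and an alpha. But the primary outcome merges fluoroscopic checks with failures of other kinds, including stone extraction failures that need not involve fluoroscopy. Its failure rate is not the proportion exposed, and it says nothing about the radiation saved.

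Third, the zeros concern DSC-arm radiation only. They do not affect ERC-arm radiation, or duration, which is always positive. Nothing in the documents shows mean and SD to be unsuitable for those.

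Fourth, leaving secondary endpoints descriptive is legitimate, and if tables are by arm a reader can derive a risk-difference interval from the counts. That is fair for binary events. It does not help with radiation, where an interval cannot be recovered reliably from a mean and SD with many zeros. The protocol also names benefits besides radiation, such as freedom from the fluoroscopy room, so a finding of non-inferior clearance would have some value without the radiation contrast.

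**Conclusion.** The point stands as a gap in the plan for the secondary endpoints. No difference between arms, with its uncertainty, is planned for radiation, duration or harm, and the summaries named as examples would describe DSC-arm radiation poorly if used alone. The absence of a contrast is read directly from the documents and needs no assumption. The SD-to-mean ratios of 2.4 to 6.2 rest on an assumed exposed share of 5% to 30% and an assumed coefficient of variation of 1. The safety half-widths rest on assumed event rates of 5% and 10% and on 125 analysed patients per arm. The primary test and the sample size are unaffected. The matter should be settled before analysis, but it does not threaten the main conclusion.

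**What to change.** Amend SAP 5.1 before analysis, by the route in SAP 5.10:

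1. By arm, report the proportion of patients with any pre-validation fluoroscopy with an exact 95% interval, and the median, quartiles and range of each radiation measure among those exposed.
2. Report the between-arm difference in mean for each radiation measure with a bootstrap 95% interval, and the between-arm difference in duration with a 95% interval (Hodges-Lehmann or bootstrap).
3. For serious adverse events, and for any cholangitis, pancreatitis, perforation or bleeding (all cases are already collected under Protocol 8.7 and 17.1), report the per-patient risk difference with a 95% interval.
4. Label all of these as estimation, with no alpha claim.
5. State how radiation and duration are counted for patients who never reach stone clearance and for DSC patients who cross over. Both windows end at completed clearance, so the differences in item 2 are undefined for some patients until this is settled.

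The cost is SAP wording and a few extra tables from data already collected. The drawback is that wide safety intervals become visible.
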